4.3.7. Late Toxicity Definition and Management

Significant AEs considered to be related to the study intervention or treatment under investigation that occur after the DLT observation period will be reviewed in the context of all available safety data.

The details of the potential late onset toxicity will be reviewed during dose level review meetings to inform decisions about enrollment and dosing (eg, dose level increments, determination of the dose(s) used beyond dose escalation, regimen). Late onset toxicities that meet the definition of DLT will be considered in the evaluation of the MTD, Phase 1 RDE and/or RP2D, as appropriate.

The option for dose reduction will be discussed with any given participant that is on-treatment at dose levels that are subsequently considered to be above the MTD. If a participant tolerated the above-MTD dose level well and is benefiting from therapy, continuation of treatment at the above-MTD dose level will require re-consenting.

4.3.8. Maximum Tolerated Dose (MTD) Definition

MTD is defined as the highest dose with true DLT rate within the target toxicity interval. The target interval for the DLT rate is defined as 0.16, 0.33.

The safety of each cohort will be assessed by a Dose Level Review Committee, which is composed of sponsor representatives and the Investigators. The Committee will consider all relevant clinical data, including safety, PK, efficacy, and PD in making decisions such as whether to dose escalate, dose de-escalate, dose level increments, expand cohorts, and declare MTD.

4.3.9. Recommended Phase 2 Dose (RP2D) Definition

The RP2D is the dose chosen for further investigation based on Phase 1 study results. The RDE is the dose chosen for further investigation based on Part 1 dose escalation results. If the MTD proves to be clinically feasible for long-term administration in a reasonable number of participants, then this dose becomes the RDE. However, RDE might be lower than the MTD. Safety, efficacy, and PK data as well as potential exposure-response relationships will be considered in identifying the RDE. After expansion cohorts with larger sample size and sufficient data, the final “Study” RP2D will be determined by the sponsor based on the recommendation from investigators and study team. The determination of “Study” RP2D will be based on safety, tolerability and early signs of clinical efficacy and benefit from both Part 1 dose escalation and Part 2 expansion.

The dose(s) selected for use in the expansion cohorts will be referred to as the Phase 1 Expansion Dose(s).

4.4. End of Study Definition

The end of the study is defined as 2 years from the last participant's first dose unless otherwise notified by the sponsor.

Accrual may be halted and a thorough safety analysis will be conducted and submitted to FDA in the event of significant safety concerns (eg, one Grade 5 SAE or two Grade 4 events considered at least possibly related to PF-07260437).

A participant is considered to have completed the study if he/she has completed all periods of the study, including the last scheduled procedure shown in the **SOA** which for Part 1 is the 4-week follow-up visit and for Part 2 is the OS follow-up.

5. STUDY POPULATION

This study can fulfill its objectives only if appropriate participants are enrolled. The following eligibility criteria are designed to select participants for whom participation in the study is considered appropriate. All relevant medical and nonmedical conditions should be taken into consideration when deciding whether a particular participant is suitable for this protocol.

Prospective approval of protocol deviations to recruitment and enrollment criteria, also known as protocol waivers or exemptions, is not permitted.

5.1. Inclusion Criteria

Participants are eligible to be included in the study only if all of the following criteria apply:

Age and Sex:

1. Participants ≥ 18 years.
 - a. Refer to [Appendix 4](#) for reproductive criteria for male ([Section 10.4.1](#)) and female ([Section 10.4.2](#)) participants.

Type of Participant and Disease Characteristics:

2. Participants who are willing and able to comply with all scheduled visits, treatment plan, laboratory tests, lifestyle considerations, and other study procedures.
3. Primary disease:

Part 1: Histological or cytological diagnosis of locally advanced or metastatic BrCa, endometrial cancer and OvCa that is resistant to standard therapy or for which no standard therapy is available. Participants with other advanced or metastatic solid tumors with high B7-H4 expression may be considered after discussion with and approval by sponsor. Similarly, those participants with other advanced or metastatic solid tumors should be resistant to standard therapy or have no available standard therapy.

Part 2A: 2L+ participants with histological or cytological diagnosis of locally advanced or metastatic HR+ HER2- BrCa showing high B7-H4 expression (see [Section 8.6.2.1](#)) who have progressed after at least 1 line of SOC CDK4/6 inhibitor and 1 line of SOC endocrine treatment. De novo paired pre- and on-treatment biopsies are mandatory for approximately 5 participants.

Part 2B: 2L+ participants with histological or cytological diagnosis of locally advanced or metastatic HR+ HER2- BrCa who have progressed after at least 1 line of SOC CDK4/6 inhibitor and 1L of SOC endocrine treatment, or 2L+ TNBC who have progressed after at least 1L of SOC systemic therapy (eg, 1L chemotherapy in

combination with a checkpoint inhibitor if PD-L1 positive or chemotherapy alone if PD-L1 negative/low). De novo paired pre- and on-treatment biopsies are mandatory for approximately 5 HR+ HER2- BrCa and 5 TNBC participants. No biomarker selection based on B7-H4 expression is needed for Part 2B.

Part 2C: 2L+ participants with histological or cytological diagnosis of locally advanced or metastatic TNBC showing high B7-H4 expression (see [Section 8.6.2.1](#)) who have progressed after at least 1L of SOC chemotherapy and 1 line of SOC systemic therapy (eg, chemotherapy in combination with a checkpoint inhibitor if PD-L1 positive or chemotherapy alone if PD-L1 negative/low). De novo paired pre- and on-treatment biopsies are mandatory for approximately 5 participants.

4. Participants have at least 1 measurable lesion as defined by RECIST version 1.1 that has not been previously irradiated. For Part 1 dose escalation, participants with metastatic HR+ HER2- breast cancer with non-measurable but evaluable disease may be eligible after discussion with and approval from the sponsor.
5. Participants must be able to provide archival FFPE material containing tumor that is of diagnostic quality and representative of their diagnosed malignancy or consent to undergo a fresh biopsy during screening. 10 participants enrolling in Part 2B, and 5 participants enrolling in each of Parts 2A and 2C must agree to paired pre- and on-treatment biopsies. Ability of a participant to undergo biopsy safely should be determined during screening. Exceptions that biopsies cannot be obtained due to safety risk should be discussed and approved by the sponsor.
6. Participants with HR+ HER2- advanced or metastatic BrCa must have:
 - a. Documentation of ER or PR-positive tumor ($\geq 1\%$ positive stained cells) based on most recent tumor tissue utilizing an assay consistent with local standards and ASCO/CAP guidelines ([Allison et al, 2020](#))
 - b. Documentation that tumor is HER2-negative as determined by IHC score of 0/1+ or negative by *in situ* hybridization (FISH/CISH/SISH/DISH) defined as HER2/CEP17 ratio < 2 or for single probe assessment a HER2 copy number < 4 , consistent with ASCO/CAP guidelines ([Wolff et al, 2018](#)).
7. Participants with TNBC must have documentation that tumor tissue is negative ($< 1\%$ cells with nuclear positivity) for ER and PR as well as negative for HER2 as determined by IHC score of 0/1+ or negative by ISH (FISH/CISH/SISH/DISH) defined as a HER2/CEP17 ratio < 2 or for single probe assessment a HER2 copy number < 4 , consistent with ASCO/CAP guidelines ([Wolff et al, 2018; Allison et al, 2020](#)).

Informed Consent:

8. Capable of giving signed informed consent as described in [Appendix 1](#), which includes compliance with the requirements and restrictions listed in the ICD and in this protocol.

Other Inclusion criteria:

9. ECOG PS 0 or 1.
10. Adequate Bone Marrow Function, defined as:
 - a. ANC $\geq 1,500/\text{mm}^3$ or $\geq 1.5 \times 10^9/\text{L}$;
 - b. Platelets $\geq 100,000/\text{mm}^3$ or $100 \times 10^9/\text{L}$;
 - c. Hemoglobin $\geq 9 \text{ g/dL}$.
11. Adequate Renal Function, as follows:
 - a. Serum creatinine $\leq 1.5 \times \text{ULN}$ or estimated CrCl $\geq 50 \text{ mL/min}$ as measured or calculated using the Cockcroft Gault formula below:
 - Female CrCl = $[(140 - \text{age in years}) \times \text{weight in kg} \times 0.85] / [72 \times \text{serum creatinine in mg/dL}]$;
 - Male CrCl = $[(140 - \text{age in years}) \times \text{weight in kg} \times 1.00] / [72 \times \text{serum creatinine in mg/dL}]$;
 - b. If an estimated CrCl is believed to be inaccurate for a participant, 24-hour urine collection with actual assessment of CrCl is allowed.
12. Adequate Liver Function, defined as:
 - a. Total bilirubin $\leq 1.5 \times \text{ULN}$ unless the participant has documented Gilbert's syndrome;
 - b. AST and ALT $\leq 2.5 \times \text{ULN}$; $\leq 5.0 \times \text{ULN}$ if there is liver involvement by the tumor;
 - c. Alkaline phosphatase $\leq 2.5 \times \text{ULN}$ ($\leq 5 \times \text{ULN}$ in case of bone or liver metastasis).
13. Participants with brain metastases must meet all the following conditions:
 - a. Have completed their planned course of treatment;
 - b. Have recovered from the acute effects of radiation therapy or surgery prior to first dose;
 - c. Have discontinued corticosteroid treatment for these metastases for at least 4 weeks;
 - d. Have been on stable doses of anti-seizure medications (if applicable) for at least 3 months. Antiseizure medications must meet any eligibility criteria outlined for concomitant medications.
 - e. Are neurologically stable for 3 months since the conclusion of therapy, as documented by both neurologic and MRI examinations.

- f. Participants who are diagnosed with a CNS metastasis during the screening period must also meet these criteria.
14. Resolution of acute effects of any prior therapy to either baseline severity or CTCAE Grade ≥ 1 (except for AEs not constituting a safety risk in the investigator's judgment).
15. TSH WNL for institution; supplementation is acceptable to achieve a TSH WNL; in participants with abnormal TSH if Free T4 is WNL and participant is clinically euthyroid, participant is eligible.
16. Negative serum or urine pregnancy test for women of childbearing potential at screening and at C1D1 (before the patient may receive the investigational product).
17. Male patients who are able to father children, and female patients of childbearing potential and at risk for pregnancy must agree to use 2 highly effective methods of contraception throughout the study and for at least 5 months after the last dose of assigned treatment.
18. Female patients who are not of childbearing potential as defined below, are eligible to be included (ie, meet at least 1 of the following criteria):
 - a. Have undergone a documented hysterectomy and/or bilateral oophorectomy;
 - b. Have medically confirmed ovarian failure; or
 - c. Achieved postmenopausal status, defined as follows: cessation of regular menses for at least 12 consecutive months with no alternative pathological or physiological cause; a serum FSH level within the laboratory's reference range for postmenopausal women.
 - d. Participants who are willing and able to comply with all scheduled visits, treatment plan, laboratory tests, lifestyle considerations, and other study procedures.

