6.5.2. Dose Delays

Re-treatment following treatment interruption for treatment-related toxicity or at the start of any new cycle may not occur until all of the following parameters have been met:

- ANC $\geq 1,000/\text{mm}^3$.
- Platelets count $\geq 50,000/\text{mm}^3$.

Nonhematologic toxicities have returned to baseline or Grade ≤ 1 severity (or, at the investigator's discretion, Grade ≤ 2 if not considered a safety risk for the participant).

If a treatment delay results from worsening of hematologic or biochemical parameters, the frequency of relevant blood tests should be increased as clinically indicated.

If these conditions are met within 4 weeks of treatment interruption, PF-07260437 may be resumed. Refer to the Dose Reductions Section 6.5.3 for AEs requiring dose reduction at the time of treatment resumption.

If participants require discontinuation of PF-07260437 for more than 4 weeks at any time during the study, then study treatment should be permanently discontinued, unless the investigator's benefit/risk assessment suggests otherwise after discussion with the sponsor. In this situation, if a treatment interruption continues for more than 4 weeks, the day when treatment is restarted will be counted as Day 1 of the next cycle.

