- When an AE or SAE occurs, it is the responsibility of the investigator to review all documentation (eg, hospital progress notes, laboratory reports, and diagnostic reports) related to the event.
- The investigator will then record all relevant AE or SAE information in the CRF.
- It is not acceptable for the investigator to send photocopies of the participant's medical records to Pfizer Safety in lieu of completion of the CT SAE Report Form/AE or SAE CRF page.
- There may be instances when copies of medical records for certain cases are requested by Pfizer Safety. In this case, all participant identifiers, with the exception of the participant number, will be redacted on the copies of the medical records before submission to Pfizer Safety.
- The investigator will attempt to establish a diagnosis of the event based on signs, symptoms, and/or other clinical information. Whenever possible, the diagnosis (not the individual signs/symptoms) will be documented as the AE or SAE.

Assessment of Severity

The investigator will make an assessment of severity for each AE reported during the study and assign it to 1 of the categories listed below (as defined by the NCI CTCAE system). An event is defined as “serious” when it meets at least 1 of the predefined outcomes as described in the definition of an SAE, NOT when it is rated as severe.

GRADE	Clinical Description of Severity
1	MILD AE
2	MODERATE AE
3	SEVERE AE
4	LIFE-THREATENING; urgent intervention indicated
5	DEATH RELATED TO AE

Assessment of Causality

- The investigator is obligated to assess the relationship between study intervention and each occurrence of each AE or SAE. The investigator will use clinical judgment to determine the relationship.
- A “reasonable possibility” of a relationship conveys that there are facts, evidence, and/or arguments to suggest a causal relationship, rather than a relationship cannot be ruled out.
- Alternative causes, such as underlying disease(s), concomitant therapy, and other risk factors, as well as the temporal relationship of the event to study intervention administration, will be considered and investigated.
- The investigator will also consult the IB and/or product information, for marketed products, in his/her assessment.
- For each AE or SAE, the investigator must document in the medical notes that he/she has reviewed the AE or SAE and has provided an assessment of causality.

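### Inclusion criterion 14 prints a floor (Grade ≥ 1) where a ceiling on residual toxicity is implied, so by itself it excludes no one for excess residual toxicity

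*Protocol*

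**What the plan says.** Criterion 14 in Protocol Section 5.1 asks for "Resolution of acute effects of any prior therapy to either baseline severity or CTCAE Grade" ≥ 1; the limit, with its sign, is printed as "baseline severity or CTCAE Grade ≥ 1". A bracketed clause then relaxes this: "except for AEs not constituting a safety risk in the investigator's judgment".

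The criterion is binding. The section opens with "Participants are eligible to be included in the study only if all of the following criteria apply", and Section 5 says that prospective approval of departures from the enrolment criteria, "also known as protocol waivers or exemptions, is not permitted".

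The severity scale is in the table in Section 10.3.3. Grade 3 is severe, and Grade 4 is described as "LIFE-THREATENING; urgent intervention indicated".

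For dosing after a toxicity interruption or at the start of a new cycle, Section 6.5.2 has a recovery rule that points the other way: "Nonhematologic toxicities have returned to baseline or Grade ≤ 1 severity". The same sentence allows Grade ≤ 2 at the investigator's discretion when that is not thought to be a safety risk.

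**The concern.** An entry rule about resolution of toxicity should say how much may remain. Criterion 14 as printed says how much must remain at a minimum. Its exception points the same way: it frees harmless events from a limit, which is useful only if the limit is an upper one.

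At stake is who may enter a first-in-human study of a T-cell engager after earlier anticancer therapy. Because waivers are barred, the printed words govern. A site that applies the evident intent departs from the text. A site that applies the text can enrol a patient with unresolved toxicity and no deviation is recorded. In a multi-center study the two readings can coexist.

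**Working it through.** No figure in the plan depends on this point and no formula applies. The check is logical: test each residual grade against the printed condition, compare the direction with the protocol's other recovery rules, and see what else screens residual toxicity at entry.

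**Step 1. Residual grades against the printed limit of Grade ≥ 1**

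| Residual grade | Meets Grade ≥ 1? |
|---|---|
| 0 (fully resolved) | No; qualifies only through the baseline-severity limb |
| 1 (mild) | Yes |
| 2 (moderate) | Yes |
| 3 (severe) | Yes |
| 4 (life-threatening) | Yes |

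The two limbs are joined by *or*, so meeting either is enough. All four grades that represent residual toxicity pass and none fails. The exception clause then has nothing left to exempt. Full recovery is the only state that does not meet the graded limb.

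**Step 2. Direction of the other recovery rules**

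- Section 6.5.2, non-hematologic recovery before re-treatment: baseline or Grade ≤ 1, with Grade ≤ 2 at investigator discretion.
- Section 6.5.3, reduced dose after recurrent intolerable Grade 2 toxicity: Grade ≤ 1 or baseline.
- Section 6.5.3, Table 10, after Grade 3 or 4 toxicity other than pancreatitis: Grade < 1 (non-hematologic) or Grade < 2 (hematologic), or baseline.
- Section 10.8.4, restart after SARS-CoV2 infection: symptoms at ≤ Grade 1.

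All are upper limits; only criterion 14 runs the other way. The limits differ in value.

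**Step 3. Is there a second copy that corrects the sign?** The key criteria in the synopsis (Section 1.1) omit criterion 14, so there is none.

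**Step 4. What else screens residual toxicity at entry**

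- Section 5.1, criteria 9 to 13: ECOG 0 or 1; marrow, renal and liver limits; recovery from radiation or surgery in patients with brain metastases.
- Section 5.2, exclusion 5: earlier Grade ≥ 3 immune-mediated events that needed immunosuppression.
- Exclusion 7: conditions or laboratory abnormalities that raise risk or make the patient unsuitable in the investigator's view. It has no grade limit.
- Exclusions 10, 12 and 13: washouts for systemic therapy, surgery and radiation. For most systemic therapy this is the shorter of 4 weeks and 5 half-lives.
- Exclusions 17 to 19: active infection, ECG findings and cardiac history.

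None of these is a general, graded limit on toxicity left over from prior therapy. A severe effect that none of the specific limits reaches, such as neuropathy, is tested only by exclusion 7.

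**The case against.** **The symbol may not be the sponsor's.** The point turns on one character, and extraction from a PDF can corrupt one. Other inequalities in the text are unstable: the stopping-rule probability is printed differently in Protocol Sections 4.3.5 and 9.3.2 and in SAP Section 3.1. Against that, the ≤ sign is printed correctly in criteria 11 and 12, just above criterion 14. An extraction fault is possible but not shown, so the source should be checked first.

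**Sites will read it as intended.** Probably many will, since the wording shows a sign slip rather than a choice. That lowers the likelihood of harm. It does not repair a binding criterion that cannot be waived.

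**Other criteria do the work.** This largely stands. A reader might infer that the protocol as a whole admits anyone with unresolved severe toxicity. The documents do not support that: the screens in Step 4 remove some of these patients. The gap is what falls outside the specific limits and rests on exclusion 7.

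**DLT attribution is already protected.** A reader might also infer that the primary Part 1 endpoint is confounded. Section 4.3.6 leaves out events reasonably attributed to preexisting conditions and requires a clinically significant shift when a baseline abnormality worsens. Section 4.3.6.3 repeats the shift requirement, and the schedules of assessment record baseline signs and symptoms at screening and on Cycle 1 Day 1. What stands is narrower. More residual toxicity puts more events into that judgment, in cohorts of about 3 with as few as 1 DLT-evaluable participant in the earliest (Sections 4.1 and 4.3.5). This is secondary and only partly handled.

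**Section 6.5.2 does not supply the answer.** This is correct. It governs re-dosing rather than entry, covers non-hematologic events in the sentence at issue, and holds two ceilings. It shows the usual direction of a recovery rule; it does not fix the grade for criterion 14.

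**Conclusion.** The criterion is wrong as printed. Taken alone, it fails none of the four residual grades, 1 to 4, and so cannot exclude anyone for excess residual toxicity. Because it is the only general graded recovery requirement at entry, severe residual toxicity that the specific limits do not reach depends on investigator judgment under exclusion 7.

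The consequence is bounded. The documents give no figure for how many candidates carry such toxicity, so the number affected cannot be estimated. No sample size, BLRM specification, estimand or analysis changes. The wider inferences, that the study as a whole is open to all severe carried-over toxicity or that DLT assessment is compromised, go beyond the text.

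The conclusion assumes that the printed symbol matches the source PDF and that sites apply the criterion as written. It does not depend on which maximum grade the sponsor meant. It merits correction as an internal inconsistency in an operative eligibility rule.

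**What to change.** Check the symbol in the source PDF. If it is as printed, amend criterion 14 so that it states a maximum residual grade, keeping the baseline alternative and the safety-risk exception if the sponsor wants them. The sponsor must state the intended grade and reconcile it with Sections 6.5.2, 6.5.3 and 10.8.4, which do not all use the same limit; where entry and re-treatment limits are meant to differ, say so.

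The cost is one symbol, or one short phrase if the grade also changes, in a protocol amendment. No SAP change is needed.

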5.2. Exclusion Criteria

Participants are excluded from the study if any of the following criteria apply:

Medical Conditions:

1. Participants with any other active malignancy within 3 years prior to enrollment. Participants with secondary malignancy that had been adequately treated, or indolent tumors that would not interfere with safety and efficacy assessments might be allowed after discussion with and approval from the sponsor.
2. Participants with advanced/metastatic, symptomatic, visceral spread, that are at risk of life-threatening complications in the short term (including participants with massive uncontrolled effusions [pleural, pericardial, peritoneal], pulmonary lymphangitis, and over 50% liver involvement). Note: Participants with indwelling

catheter for drainage, or requirement for drainage no more frequently than monthly will be allowed.

3. Clinically important (eg, 150/90 mmHg) hypertension despite optimal medical therapy.
4. Known or suspected hypersensitivity to PF-07260437 or excipients.
5. History of Grade ≥ 3 immune mediated AE (including AST/ALT elevations that were considered drug related and cytokine release syndrome) that was considered related to prior immune modulatory therapy (eg, immune checkpoint inhibitors, co stimulatory agents, etc.) and required immunosuppressive therapy within 1 year of treatment. Participants with Grade 2 hypothyroidism or hypopituitarism resulting from immunotherapy on stable hormone replacement therapy and participants with chronic adrenal insufficiency receiving doses < 10 mg/day of prednisone equivalents are eligible.
6. Prior irradiation to $> 25\%$ of the bone marrow (see [Appendix 10](#), Bone Marrow Reserve in Adults).
7. Other medical or psychiatric condition including recent (within the past year) or active suicidal ideation/behavior or laboratory abnormality that may increase the risk of study participation or, in the investigator's judgment, make the participant inappropriate for the study.

Prior/Concomitant Therapy:

8. Current use of any prohibited concomitant medication(s) or those unwilling/unable to use a permitted concomitant medication(s). Refer to [Section 6.8](#), Concomitant Therapy.
9. Therapeutic anticoagulation with high bleeding risk or active bleeding.
10. Systemic anti-cancer therapy chemotherapy or endocrine therapy within 4 weeks or 5 half-lives (whichever is shorter) prior to first dose (6 weeks for mitomycin C or nitrosoureas). If the last immediate anticancer treatment contained an antibody-based agent(s) (approved or investigational), then an interval of 3 weeks or 5 half-lives (whichever is shorter) of the agent(s) prior to receiving the study intervention treatment is required.
11. Requirement for systemic immune suppressive medication [eg, ≥ 10 mg of prednisone or equivalent (≥ 1.5 mg of dexamethasone)]. Inhaled, intranasal, intraocular, intraarticular, and topical corticosteroids are allowed.
12. Major surgery within 3 weeks prior to first dose or during the study. Minor surgery may be allowed after consultation with and approval from sponsor.

13. Radiation therapy within 3 weeks prior to first dose or during the study. Palliative radiation to a limited field may be allowed after consultation with and approval from sponsor.

Blood product support:

14. Requirement for periodic blood product transfusions for a chronic condition. Blood product transfusions for transient and reversible cytopenias that are secondary to prior anti-cancer treatment are allowed after discussion with the sponsor.

Prior/Concurrent Clinical Study Experience:

15. Participation in other studies involving investigational drug(s) within 3 weeks or 5 half-lives (whichever is shorter) prior to first dose. A participant may be eligible even if they are in the follow-up phase of an investigational study as long as they haven't received treatment in the study for 4 weeks of 5 half-lives prior to first dose.

Diagnostic Assessments:

16. Serum or urine pregnancy test (for females of childbearing potential) positive at screening.
17. Participants with active, uncontrolled bacterial, fungal, or viral infection, including (but not limited to) HBV, HCV, COVID-19/SARS-CoV2, and known HIV or AIDS-related illness. Comments regarding specific circumstances follow:
 - a. COVID-19/SARS-CoV2: This protocol excludes patients with active infections, as noted above. While SARS-CoV2 testing is not mandated for entry into this protocol, testing should follow local clinical practice standards. If a patient has a positive test result not from prior COVID vaccination but from SARS-CoV2 active infection (not from prior vaccination but from active infection), is known to have asymptomatic infection or is suspected of having SARS-CoV2, he/she is excluded. COVID-19 vaccine administration relative to the dosing of study drug on planned C1D1 is at the discretion of the investigator although it may be best to avoid administration the 7 days prior to C1D1 and consider the potential for vaccine-related adverse events.
 - b. HIV: In equivocal cases, participants whose viral load is negative may be eligible. HIV seropositive participants who are otherwise healthy and at low risk for AIDS-related outcomes could be considered eligible. Potential eligibility for a specific HIV positive protocol candidate should be evaluated and discussed with the sponsor prior to any screening, based on current and past CD4 and T cell counts, history (if any) of AIDS defining conditions (eg, opportunistic infections), and status of HIV treatment. Healthy HIV positive participants who are included should be treated using the same standards as trial participants with other comorbidities.

- c. HBV/HCV: Relevant laboratory tests should be performed at screening, see table in [Appendix 2](#). Refer to CDC website (<https://www.cdc.gov/hepatitis/index.htm>) for further details.
- d. HBV:
 - This criterion excludes participants with a positive HBsAg (ie, either acute or chronic active hepatitis).
 - However, participants with HBV antibody positivity indicating immunity, either due to vaccination or prior natural infection, are eligible.
 - Patients with positive anti-HBcAb but negative HBsAg and anti-HBsAb profile may, depending on clinical circumstances, be eligible. Discussion with the sponsor is indicated. Patients whose clinical history and profile suggest either low level chronic infection or resolving acute infection should not be considered eligible.
- e. HCV:
 - Positive HCV antibody is indicative of infection but may not necessarily render a potential candidate ineligible, depending on clinical circumstances. Discussion with the sponsor is indicated. If exposure to HCV is recent, HCV antibody may not have yet turned positive. In this circumstance it is recommended to test for HCV RNA. Refer to CDC website for further details (https://www.cdc.gov/hepatitis/hcv/pdfs/hcv_graph.pdf).

18. Baseline standard 12-lead ECG that demonstrates clinically relevant abnormalities that may affect participant safety or interpretation of study results (eg, baseline QTcF>470 ms, complete LBBB, signs of an acute or indeterminate age- myocardial infarction, ST-T interval changes suggestive of active myocardial ischemia, second or -third-degree AV block, or serious brady arrhythmias or tachyarrhythmias). If the baseline uncorrected QTcF is >470 ms, this interval should be rate corrected using the Fridericia method and the resulting QTcF- should be used for decision making and reporting. QTcF exceeds 470 ms, or QRS complex exceeds 120 ms, the ECG should be repeated 2 more times and the average of the 3 QTcF or QRS complex values should be used to determine the participant's eligibility. Computer interpreted-ECGs should be over-read by a physician experienced in reading ECGs before excluding participants. Cases must be discussed in detail with the sponsor to judge eligibility.

19. Any of the following in the previous 6 months: myocardial infarction, long QT syndrome, Torsade de Pointes, clinically important atrial or ventricular arrhythmias (including sustained ventricular tachyarrhythmia and ventricular fibrillation), serious conduction system abnormalities (eg, bifascicular block [defined as right bundle branch and left anterior or posterior hemiblock], 3rd degree AV block), unstable angina, coronary/peripheral artery bypass graft, symptomatic CHF, New York Heart Association Class III or IV, cerebrovascular accident, transient ischemic attack, symptomatic pulmonary embolism, and/or other clinical significant episode of

thrombo-embolic disease. Ongoing cardiac dysrhythmias of NCI CTCAE \geq Grade 2, atrial fibrillation of any grade (\geq Grade 2 in the case of asymptomatic lone atrial fibrillation). If a participant has a cardiac rhythm device/pacemaker placed and QTcF >470 ms, the participant may be considered eligible. Participants with cardiac rhythm device/pacemaker must be discussed in detail with the sponsor to judge eligibility.

Other Exclusions:

20. Investigator site staff or Pfizer employees directly involved in the conduct of the study, site staff otherwise supervised by the investigator, and their respective family members.

